## Section H: Potential Risks/Discomforts

### H1. Potential Risks/Discomforts

Describe and assess any potential risks/discomforts; (physical, psychological, social, legal, or other) and assess the likelihood and seriousness of such risks:

Overall, the risks of this study are considered relatively minor. One potential risk of participating in this study is discomfort associated with the psychiatric evaluation and completion of rating scales-- either due to the discussion of subjectively difficult topics or due to the length of time required for the interviews and questionnaires. However, we have found that most people welcome the opportunity to discuss their experiences with a trained clinician; and breaks will be given as much as possible to decrease boredom and physical/psychological discomfort. In rare cases, psychotherapy may exacerbate anxiety symptoms. Should a child's symptoms increase significantly (linked to treatment or not) and require study discontinuation, we will discuss alternative treatment options including psychotropic medication and more intensive psychotherapy. We will implement very strict rescue criteria should a child's symptoms worsen significantly; he/she requires a higher standard of care (i.e., inpatient); and/or the child experiences suicidality or significant side effects. Should a participant's symptoms markedly worsen, and/or the individual experience suicidality or significant side effects, he/she will be immediately withdrawn from the study and provided with the standard of care, which may include hospitalization, if necessary. [name] and [name] (or a covering clinician) will be available at all times to study participants in the event of a clinical emergency. Both this availability and how to reach the investigators in an emergency will be clearly communicated orally and in writing to study participants.

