**ASSESSMENTS.** All participants will be asked to cooperate in assessments that will occur at pre-treatment (baseline before treatment), post-treatment (at the end of the twelve weeks), and 1-month follow up (4 weeks after first 12 weeks of treatment have concluded). Non-responders to bibliotherapy (assessed at 1-month follow-up) who choose to participate in therapist-led SPACE will complete an additional post-treatment assessment following up to eight additional sessions of SPACE (up to 8 weeks later). The three assessments include a battery of questionnaires and measures at these three timepoints. Depending on group assignment (LTC-SPACE or standard SPACE), measures will also be completed at session visits. Treatment responder status will be assessed at the 1-month follow up, and whether participants in the LTC-SPACE group receive up to 8 additional weeks of standard SPACE will be determined based on the 1-month follow up assessment.

The IE will be an experienced clinician, trained professional, or advanced graduate trainee (supervised by a clinician). The measures that will be administered will include both IE-rated and participant-rated scales (please see attachment in section S). Measures will be completed either in-person or by secure connection (Zoom) and Qualtrics, to reduce burden.

**TREATMENT FIDELITY/INTEGRITY.** All clinician and assessment sessions, in both conditions, will be audio-recorded or video-recorded (with parent consent). These recordings will be used for research purposes, to monitor ongoing fidelity, to quantify treatment adherence, as well as to assess inter-rater reliability and rater drift. If concerns are noted, the clinician and/or IE will not conduct another assessment until procedures have been reviewed. Clinicians will upload audio and video recordings to a web-secure, HIPAA-compliant storage (Box). Fidelity measures have been developed in our pilot work and adapted for use in this project: [1] The Parent Completion and Effort Rating (PCER); and [2] The Treatment Adherence, Content, and Competence Checklist. We will also use treatment fidelity checklists for each session following Lebowitz et al. (2020).

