## Section G: Sample Size/Data Analysis

### G1. Sample Size

How many subjects (or specimens, or charts) will be used in this study?

Local: 240      Worldwide: 240

Please indicate why you chose the sample size proposed:

We will enroll 120 parent-child dyads (n = 240 total children and parents), we anticipate 90 dyads will be eligible (n = 180), in order to meet an intent-to-treat sample size of 45 parent-child dyads per group, accounting for screen-fail rates. This exceeds our anticipated needs of 34 parent-child dyads per group to detect statistical significance in response rates on the CGI-I, the primary outcome measure. The power analysis assumed  $\alpha = .05$ , power = .95, as well as a 24% response rate for the parent self-guided intervention (based on our previous work with a similar approach; Storch et al., under review) and a 66% response rate for individual SPACE based on the Lebowitz et al. (2020) trial. We also anticipate the target sample size will be more than enough to detect differences in reductions on the Pediatric Anxiety Rating Scale (PARS), our other primary outcome, based on the Lebowitz et al. (2020) trial and our own preliminary analysis (Storch et al., under review). For this outcome, we anticipate needing 16 participants to detect statistically significant differences. This assumes an effect size of  $f = .845$ ,  $\alpha = .05$ , power = .95, and a correlation among repeated measures of  $r = .33$ .

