### G2. Data Analysis

Provide a description of your plan for data analysis. State the types of comparisons you plan (e.g. comparison of means, comparison of proportions, regressions, analysis of variance). Which is the PRIMARY comparison/analysis? How will the analyses proposed relate to the primary purposes of your study?

Descriptive statistics on all randomized participants will be analyzed and if any key variables (e.g. anxiety severity) differ across groups, they will be controlled for in analytic models via inclusion as a covariate. Violations of distributional assumptions will be addressed (e.g. robust sandwich estimators and interval smoothing for continuous variables, and exact logistic regression) in the case of sparingly distributed dichotomous dependent variables.

Study Aims 1-4 address pre-post group differences as a result of treatment, statistical moderation of pre-post treatment effects, and evaluation of additional observed change from post-treatment to 1-month follow up. Chi-square analyses will compare dichotomous outcomes (i.e., treatment response rates). Mixed within-between (time by treatment group) analysis of covariance (ANCOVA) will be used to assess pre-post and post-1-month follow up changes in continuous outcomes (i.e., symptom severity). Within-group change on continuous measures from post-treatment to 1-month follow up will be assessed by dependent t-tests for each treatment group. Between group differences in study dropout will be assessed by logistic regression.

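### Children who worsen are withdrawn from the study itself, so CGI-I and PARS can be missing because of poor outcome, and the named tests would in practice drop those dyads

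*Combined protocol and SAP*

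**What the plan says.** **Withdrawal (H1).** The triggers are set out as "Should a participant's symptoms markedly worsen, and/or the individual experience suicidality or significant side effects", and the consequence is that "he/she will be immediately withdrawn from the study and provided with the standard of care". The same section expects treatment-caused worsening to be uncommon: "In rare cases, psychotherapy may exacerbate anxiety symptoms". It gives no rate for that or for the other triggers.

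**Assessments (F2, Assessments).** "All participants will be asked to cooperate in assessments that will occur at pre-treatment", at the end of the twelve weeks, and again four weeks later. Remote completion is allowed: "Measures will be completed either in-person or by secure connection (Zoom) and Qualtrics, to reduce burden". Some measures are also taken at session visits, but the text does not name them. It does not say whether the two later assessments are still offered to a child withdrawn under H1. H2 refers to a separate data and safety monitoring attachment, which is not among the supplied documents.

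**Sample size (G1).** Enrolment is set "in order to meet an intent-to-treat sample size of 45 parent-child dyads per group", with an allowance for screen failures. CGI-I response and PARS are both called primary outcomes.

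**Analysis (G2).** "Descriptive statistics on all randomized participants will be analyzed", and baseline imbalances are to be adjusted for. "Chi-square analyses will compare dichotomous outcomes (i.e., treatment response rates"), and a time-by-group mixed ANCOVA is named for continuous outcomes. Dropout appears once, as something to compare between arms by logistic regression. No rule is given for a CGI-I or PARS that was not observed.

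**The concern.** Most missing-data comments concern families who drift away for unknown reasons. Here the protocol itself creates a route to missing outcomes that depends on the outcome. Marked worsening is close to the opposite of CGI-I response, so a child who leaves under H1 is very probably a non-responder with a poor PARS change. If follow-up ends at withdrawal, that child has no later value. A chi-square on observed responses cannot count such a child. A conventional repeated-measures ANCOVA drops any dyad without the later PARS.

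The dyads lost would then come selectively from the bad end of the distribution, in a trial whose size is stated on an intent-to-treat basis. At stake are the two primary comparisons. The observed response rate rises in any arm that loses non-responders, so the apparent difference can move up or down depending on where the withdrawals fall.

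**Working it through.** **1. The plan's own figure.** Inputs from G1: response 24% (low-contact) and 66% (standard SPACE), α = .05, power .95. Two-sided, pooled variance, no continuity correction, with mean rate (.24 + .66)/2 = .45:

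n = [1.960·√(2·.45·.55) + 1.645·√(.24·.76 + .66·.34)]² / (.66 − .24)² = (1.379 + 1.049)² / .42² = 33.4, so 34 per group.

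This matches G1. The stated 16 for PARS also reproduces if two measurements per child are assumed (between-groups F test, f = .845, r = .33: power .970 at 16 in total). The sample size is not in question.

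**2. Response difference if withdrawn children are not counted.** Let L be the share of an arm withdrawn. The documents give no value, so L is assumed. Every withdrawn child is taken to be a non-responder, which makes these figures a ceiling.

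Apparent difference = .66/(1 − L₁) − .24/(1 − L₂), with L₁ for standard SPACE and L₂ for low-contact.

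| Withdrawn | Standard SPACE only | Low-contact only | Both arms |
|---|---|---|---|
| One child (1/45 = 2.2%) | 43.5 | 41.5 | 43.0 |
| 5% | 45.5 | 40.7 | 44.2 |

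For example, .66/.95 − .24 = .4547. The planned value is 42.0 points. The shift is 0.5 to 1.5 points for one child per affected arm and 1.3 to 3.5 points at 5%. Equal loss also raises the difference, because both rates are divided by the same number below 1.

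**3. Power.** By exact enumeration with 45 per arm and an uncorrected two-sided chi-square, power is .985 with no loss. At 5% loss it is .994 (standard SPACE only), .978 (low-contact only) and .990 (both).

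**4. Type I error.** The same enumeration with equal true response rates and 5% withdrawn from one arm:

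| True rate in both arms | No loss | 5% in one arm | 5% in both arms |
|---|---|---|---|
| 24% | .054 | .053 | .051 |
| 35% | .053 | .055 | .051 |
| 45% | .046 | .056 | .051 |
| 66% | .053 | .065 | .051 |

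The change at 45% is partly discreteness: equal loss, which creates no bias under the null, already moves .046 to .051. A clear rise appears only at the high common rate.

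**5. PARS.** If the worst share L of normally distributed change scores in one arm is lost, that arm's mean shifts by φ(z_L)/(1 − L) SD. This is .109 SD at 5% and .054 SD for one child in 45.

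**6. Does scoring every missing CGI-I as non-response solve it?** For children withdrawn under H1 who are true non-responders, yes: the difference stays at 42.0. For dropout unrelated to outcome, no. At an assumed 5%:

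- standard SPACE only: .66·.95 − .24 = 38.7 points;
- low-contact only: .66 − .24·.95 = 43.2 points;
- both arms: .627 − .228 = 39.9 points, power .976.

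With a common 45% rate and such dropout in one arm only, Type I error is .051, .067 and .095 at 5%, 10% and 15% dropout. With 15% dropout in both arms, power at the planning rates is about .95. This rule's error in one arm (3.3 points at 5%) is about as large as the bias it would remove (3.5 points).

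**The case against.** G1's intent-to-treat label sits in the same paragraph as the primary outcome, and G2 opens with all randomised participants, so the natural denominator is every randomised dyad. H1 is a safety paragraph and does not say that assessments stop. F2 asks everyone to complete them, and the unsupplied monitoring attachment may settle the point. Session-visit measures may also give some data before withdrawal. Exacerbation is expected to be rare, the trial is classed as a pilot (F1), and even the ceiling figures do not overturn a 42-point effect.

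Much of this stands, and it rules out stronger conclusions that a reader might draw:

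- **That the plan specifies a completers-only analysis, or names no population.** It does neither. G1 largely answers which dyads belong in the comparison. It does not say how a dyad with no observed CGI-I or PARS enters a chi-square or an ANCOVA.
- **That follow-up certainly ends at withdrawal.** That is the plain sense of leaving the study, but it remains an inference from the supplied text.
- **That the trial loses power.** Power stays at .978 or above in every withdrawal case examined.
- **That false positives are generally inflated.** The result depends on the assumed common rate and is partly discreteness.
- **That non-response scoring is the obvious remedy.** Its own bias is comparable when ordinary dropout differs between arms.

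The core remains: H1 removes children from the study on grounds tied to the outcome, no supplied section keeps their assessments going, and the two named methods cannot use a dyad without the outcome.

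**Conclusion.** The point holds as a matter of modest, avoidable bias in the two primary comparisons. As an assumed ceiling, 5% withdrawn moves the apparent response difference from 42.0 points to between 40.7 and 45.5, and one arm's mean PARS change by at most 0.11 SD. For one child per affected arm, the range is 41.5 to 43.5 points, with a PARS shift of 0.05 SD.

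These figures rest on assumptions: a withdrawal rate that the documents do not give, every withdrawn child being a non-responder, normal change scores for PARS, no assessment after withdrawal, and the named tests being run on observed outcomes. If withdrawals are as rare as H1 suggests for treatment-caused worsening, the effect will sit at the low end. If the monitoring attachment already provides for continued assessment, only the analysis part remains.

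**What to change.** Leave the clinical withdrawal criteria as they are.

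1. **H1 and F2:** distinguish stopping study treatment from leaving the study. State that a child who stops treatment is still offered the scheduled post-treatment and 1-month CGI-I and PARS assessments, remotely if needed, provided the family agrees. If the monitoring attachment already says this, refer to it.
2. **G2, analysis set:** carry G1's intent-to-treat set into both primary tests, with dyads analysed as randomised. State in advance how values recorded after other care has begun are used.
3. **G2, PARS:** replace the ANCOVA with a likelihood-based repeated-measures model on all available data. It assumes missing at random, and a child with only a baseline value tells it little, so it complements continued follow-up and does not replace it.
4. **G2, CGI-I:** fix the handling of any value still missing before outcomes are seen, and report it with a sensitivity analysis. One option is non-response scoring beside multiple imputation by arm with a stated shift. Non-response scoring should not stand alone, for the reason shown in step 6 of the working.

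The cost is a few remote assessments that are already scheduled, some wording in the protocol, and slightly more analysis. No additional families are needed.

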### H2. Data and safety monitoring plan

Do the study activities impart greater than minimal risk to subjects?

Yes

NOTE: The answer to the questions in H2 requires the completion of the form: 'Section H â€“ Data and Safety Monitoring Plan' as an attachment in Section S.

### H3. Coordination of information among sites for multi-site research

Is the BCM Principal Investigator acting as the SPONSOR-INVESTIGATOR for this multi-site research?

No or Not Applicable

Is BCM the COORDINATING CENTER for this multi-site research?

No or Not Applicable

## Section I: Potential Benefits

Describe potential benefit(s) to be gained by the individual subject as a result of participating in the planned work.

There are several anticipated benefits associated with study participation, including improved access to care, extensive psychiatric evaluation and psychological treatment. As a result of the latter, subjects may experience improvements in both quality of life and psychosocial functioning, as well as reductions in symptoms presentation and related impairment.

Describe potential benefit(s) to society of the planned work.

Participation will provide valuable treatment outcome data, which may benefit future families by helping faculty and staff better evaluate and improve treatment and care for individuals anxiety and/or OCD. Overall, understanding the effectiveness of a lower therapist contact model may also have dramatic benefits for improving access, allocating more intensive services for those most in need, and reducing barriers (e.g., distance).

Do anticipated benefits outweigh potential risks? Discuss the risk-to-benefit ratio.

The benefits of participation far outweigh the relatively minor risks of participation. The treatment provided has demonstrated non-inferiority to CBT (considered standard-of-care) in a rigorous randomized controlled trial, with 88% of participants being classified as treatment responders (n=42/48). In addition, it is possible that treatment may be rendered faster when participating in the research study given the typical wait-list period when being seen through a standard clinic.

## Section J: Consent Procedures

### J1. Waiver of Consent

Will any portion of this research require a waiver of consent and authorization?

No

#### J1a. Waiver of requirement for written documentation of Consent

Will this research require a waiver of the requirement for written documentation of informed consent?

Yes

Explain how the research involves no more than minimal risk to the participants, and the specifics demonstrating that the research does not involve procedures for which written consent is normally required outside of the research context.

The waiver of written consent is required for the pre-screening portion of the study. Verbal consent will be obtained before the pre-screening, and written informed consent will be obtained before proceeding with further study activities. Please see the script for obtaining verbal consent before the pre-screening, attached in Section S.

Collecting basic information (e.g. name, DOB, contact information, reason for seeking treatment) to determine study eligibility criteria involves no more than minimal risk to the subject. Patient information is routinely reviewed by clinicians when determining eligibility for treatment after receiving a verbal consent, and access to such information is strictly monitored. Only individuals who have been trained in health information privacy protocols are allowed to review patient information, and all investigators conducting screenings will receive the same training. Thus, a standard protocol for protecting patient's privacy rights already exists. We will review subjects' information to confirm subject eligibility. We will also review any pertinent documentation regarding prior testing (e.g., any anxiety disorder or autism spectrum disorder diagnostic assessments, IQ, genetic-testing) in order to verify subject eligibility.

### J2. Consent Procedures

Who will recruit subjects for this study?

PI  
PI's staff

Describe how research population will be identified, recruitment procedures, any waiting period between informing the prospective participant and obtaining consent, steps taken to minimize the possibility of coercion or undue influence and consent procedures in detail.

Parents will be given a 20-minute telephone screening to elicit preliminary inclusion/exclusion information, confirm potential interest, and answer any questions the parent may have about the study. A screening form will be used to collect pertinent information including contact information, basic demographics (age, race, gender ethnicity), and questions relating to mood and health. Individuals who meet basic eligibility requirements during the phone interview and remain interested will be invited for a screening visit (i.e., baseline assessment), at which point a member of the research team will obtain informed consent/assent from the parent and child.

**INFORMED CONSENT.** There are three possibilities for obtaining consent if and when a potential participant (e.g., parent and child) chooses to participate in this study.

1) Consent will be obtained in-person. Participants will be provided with all relevant information and will be given as much time as needed to decide whether to participate. The person obtaining consent will thoroughly explain each element of the document and outline the risks and benefits, alternate treatment(s), and requirements of the study. The consent process will take place in a quiet and private room, and participants may take as much time as needed to make a decision about their participation. Members of the research team will be available to answer questions or explain any details further. Participants will be informed that their participation or absence of participation will not have any influence on the clinical services received at BCM (or any other institution). Informed consent/assent will be obtained prior to proceeding with any study procedures. A copy of the informed consent form will be given to the subject to take home with them. All participants will also be informed that they do not have to answer any specific questions if they do not wish to do so.

2) Consent will be obtained using an electronic process. All regulatory consent procedures explained above will be followed when using e-consent protocol i.e. provided all relevant information and be given as much time as needed. A member of the research team will schedule an informed consent via HIPAA compliant video conferencing software, ZOOM. Participants will be provided an electronic copy of the consent to read prior to the call. Research staff will send the participant a secure e-mail link to an online consent form via Redcap. We will also provide 'key points' to the study, to aid in the parents explanation of the study to their child (attached in Section S) so that the child has an understanding of the study, requirements, and components prior to the scheduled call. During the scheduled call, participant and research team member(s) will thoroughly review the consent to ensure comprehension, answer any questions, and address any concerns. Participants will be able to agree to participate, and sign the consent form with a stylus, mouse, or finger and submit it to the research staff. The participant will also be able to download a copy of their signed consent form as a PDF through REDCap. A PDF of the online survey can be found in Section S. Also attached is a copy of the last page where name, signature, and date are collected.

3) Consent will be obtained via mail. Alternatively, participants have the option of receiving the informed consent in hard-copy via mail. The research team will mail 2 consent forms to the participant. The consent discussion will be conducted over the phone before the participant signs the forms. Members of the research team will be available to answer questions or explain any details further. The participant will be instructed to sign both, keep one for their records, and mail back the second using the self-addressed stamped envelope included in the mailing. Informed consent will be obtained prior to proceeding with any study procedures.

Are foreign language consent forms required for this protocol?

No

